As of Amendment 5, the study will have one primary objective (to demonstrate that PF-06801591 given in combination with BCG [induction and maintenance] is superior to BCG alone [induction and maintenance] in prolonging EFS in participants with high-risk NMIBC. The objective to demonstrate that PF-06801591 given in combination with BCG (induction only) is superior to BCG alone (induction and maintenance) in prolonging EFS in participants with high-risk NMIBC will be considered a key secondary objective.

In order to conduct a preliminary assessment that the safety profile of PF-06801591 plus BCG regimen remains aligned with that expected from each agent separately, a review of safety data will be performed by an external data monitoring committee (EDMC) approximately 6 weeks after 20 participants in each of the 3 arms have been randomized and received at least one dose of study treatment. The EDMC will convene to monitor safety in the study (Cohort A only) approximately every 6 months thereafter. The EDMC will also

review cumulative safety data during the study conduct as well as review the futility interim analysis (IA) data for EFS (see Section 9.5.1).

Participants who meet the following criteria will enter the post-treatment follow-up period for safety visits.

[figure not shown]
- Progression of NMIBC
- Recurrence (T1 [stage of cancer in which the cancer cells are only growing in the most superficial layer of tissues and have not grown into deeper tissues. In bladder cancer, T1 is defined as an invasion into the lamina propria without invasion into the muscularis propria], high-grade Ta [non-invasive papillary carcinoma], and/or CIS). Participants with high-grade Ta recurrence at 3 months after initiating study intervention following first induction period may receive re-induction. Following re-induction if recurrence of high-grade Ta disease occurs at 6 months of initiating study intervention, participants will discontinue study treatment and enter the post-treatment follow-up period.
- Participants with CIS at randomization that is not responding within 6 months of initiating study intervention, following induction or re-induction (persistence of CIS).
- Participants who complete or those who permanently discontinue study intervention early.

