8.1.1.1. Cystoscopy

Cystoscopy should be performed and assessed using the same method and equipment by the same study staff (whenever possible), for the duration of the study, in order to reduce subjectivity across multiple assessments. White light, blue light or narrow-band imaging are allowed in this study and blue light is preferred. Number, size and location of the tumors should be documented.

Disease status will be assessed through cystoscopy conducted at screening, every 12 weeks for 2 years following randomization, and every 24 weeks during the rest of follow-up, and as clinically indicated. Timing of disease assessment is to be fixed according to the calendar (± 7 days) starting with randomization for Cohort A and initiation of study intervention for Cohorts B1 and B2, and should not be adjusted for study intervention dose modifications. Please refer to the Schedule of Activities for disease assessment time points for each Cohort.

Cystoscopy with biopsy is required at the time of recurrence of high-grade disease, disease progression, persistence of CIS (applicable only to participants with CIS at randomization), or complete response (applicable only to participants with CIS at randomization) as described in Section 10.9.

In Cohort A, biopsy for confirmation of complete response for participants with CIS should be performed at the 24 week disease assessment, unless collection at the 12 week disease assessment is routinely performed at the given institution. Please consider that if the bladder biopsy collection at the Week 12 disease assessment fails to confirm CR, the biopsy collection must be repeated at the Week 24 disease assessment. If it is not possible to perform the bladder biopsy collection by the Week 24 disease assessment, biopsies should be collected as soon as possible at the next scheduled disease assessment.

Timing of disease assessment is to be fixed according to the calendar (± 7 days), starting with randomization for Cohort A, and initiation of study intervention for Cohorts B1 and B2, and should not be adjusted for study treatment dose modifications.

For cystoscopy without biopsy, either flexible or rigid cystoscopy may be conducted as per the Investigator's clinical judgement or institutional guidance/preference. Further specifications for the procedure are provided in the Study Manual.

For cystoscopy with biopsy, a full thickness tissue specimen is required to be obtained and Sponsor recommends a rigid cystoscopy.

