Recurrence of high-grade disease is defined as re-appearance of high-grade disease (high-grade Ta, T1 or CIS) after randomization/initiation of study intervention or re-appearance of high-grade disease after CR for participants with CIS at baseline or re-appearance of high-grade disease before CR for participants with CIS and concurrent papillary disease at baseline in Cohort A or B1. This will require a cystoscopy or cytology positive result, with biopsy positive for T1, high-grade Ta and/or CIS. The date of positive biopsy, cystoscopy, or cytology (whichever positive result is earliest) will be used as the date of recurrence of high-grade disease. In Cohort B1, if the investigator determines that high-grade disease is present, the participant may continue on study for 1 additional cycle, until BICR review confirms diagnosis of high-grade disease. At that time, if high-grade disease recurrence is confirmed by the BICR, the participant must discontinue study treatment.

Recurrence of low-grade disease is defined as re-appearance of low-grade disease (low-grade Ta) after randomization (Cohort A)/initiation of study intervention (Cohort B). This will require a cystoscopy or cytology positive result, with biopsy positive for low-grade Ta. The date of positive biopsy, cystoscopy or cytology (whichever positive result is earliest) will be used as the date of recurrence of low-grade disease.

Progression of disease is defined as any of the following:

- Lamina propria invasion (eg, increase from Ta to T1 or CIS to T1)
- Muscle invasive disease (stage \geq T2)
- Lymph node positive disease (N $+$)
- Metastatic disease (M1)
- Appearance of high-grade Ta or T1 in participants with CIS only at baseline (Cohort A and Cohort B1) before achieving a CR.

This will require a cystoscopy or cytology positive result with imaging positive and/or biopsy positive for disease progression as described above. The date of positive biopsy, imaging for new lesion, positive cystoscopy, or positive cytology (whichever positive result is earliest) will be used as the date of progression.

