### **5.2.12. Disease Assessments**

Disease will be assessed based on reported results from cytology, cystoscopy, biopsy, and imaging scans at different evaluation time points from the ‘start date’ until the first documentation of progression of disease, recurrence of high-grade disease, or persistence of CIS disease according to the following rules.

**Complete Response**, in participants with CIS at randomization (Cohort A)/baseline (Cohort B1), is defined as:

- histologic disappearance of malignancy on bladder biopsy with negative cytology and cystoscopy; or
- negative cytology and positive cystoscopy with biopsy-proven low-grade Ta lesion or non-malignant tissue.

The date of biopsy, cystoscopy, or cytology (whichever is earliest) will be used as the date of CR.

**Persistence of CIS**, in participants with CIS at randomization in Cohort A, is defined as persistence of CIS after induction or re-induction (if re-induction is administered). For participants in Cohort B1, persistence of CIS is defined as persistence of CIS at the 12-week disease assessment. This will require a cystoscopy or cytology positive result with biopsy positive for CIS. The date of positive biopsy, cystoscopy, or cytology (whichever positive result is earliest) will be used as the date of persistence of CIS.

**Recurrence of high-grade disease** is defined as re-appearance of high-grade disease (high-grade Ta, T1 or CIS) after ‘start date’ for the following 1) participants without CIS at baseline, 2) after CR for participants with CIS at baseline, or 3) before CR for participants with CIS and concurrent papillary disease at baseline in Cohort A or B1. This will require a cystoscopy or cytology positive result, with biopsy positive for T1, high-grade Ta and/or

CIS. The date of positive biopsy, cystoscopy, or cytology (whichever positive result is earliest) will be used as the date of recurrence of high-grade disease. If recurrence of high-grade disease occurs at the time of progression, progression should be the event. For participants with CIS at randomization, appearance of high-grade disease after a CR is considered recurrence of high-grade disease, while appearance of high-grade disease before a CR is progression.

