**Recurrence of low-grade disease** is defined as re-appearance of low-grade disease (low-grade Ta) after ‘start date’. This will require a cystoscopy or cytology positive result, with biopsy positive for low-grade Ta. The date of positive biopsy, cystoscopy, or cytology (whichever positive result is earliest) will be used as the date of recurrence of low-grade disease.

**Progression of disease is defined** as any of the following:

- Lamina propria invasion (e.g., increase from Ta to T1 or CIS to T1)
- Muscle invasive disease (stage  $\geq$  T2)
- Lymph node positive disease (N+)
- Metastatic disease (M1)
- Appearance of high-grade Ta or T1 in participants with CIS only at baseline (Cohort A and Cohort B1) before achieving a CR.

This will require a cystoscopy or cytology positive result with imaging positive and/or biopsy positive for disease progression as described above. The date of positive biopsy, imaging for new lesion, positive cystoscopy, or positive cytology (whichever result is earliest) will be used as the date of progression.

**No Evidence of Disease:** only applies to participants without CIS at baseline (Cohort A and Cohort B2) and is defined as disease that was completely resected prior to ‘start date’ and does not meet the criteria of progression of disease, recurrence of high-grade disease, or recurrence of low-grade disease while on study.

The date of imaging, biopsy, cystoscopy, or cytology (whichever result of the available assessments is earliest) that supports no evidence of disease will be used as the date of no evidence of disease.

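### CIS found on the planned Week 24 CR biopsy with negative cystoscopy and cytology fits no EFS category in SAP 5.2.12 or protocol Appendix 9, although Tables 2 and 10 imply that it should count

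*SAP*

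**What the plan says.** **Event definitions.** For persistence of CIS, SAP 5.2.12 states: "This will require a cystoscopy or cytology positive result with biopsy positive for CIS". Protocol Appendix 9 (section 10.9) gives the same condition. High-grade recurrence carries it too (Appendix 9): "This will require a cystoscopy or cytology positive result, with biopsy positive for T1, high-grade Ta and/or CIS". So does progression (SAP 5.2.12): "This will require a cystoscopy or cytology positive result with imaging positive and/or biopsy positive for disease progression as described above".

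**CR.** The first route in SAP 5.2.12 is "histologic disappearance of malignancy on bladder biopsy with negative cytology and cystoscopy; or". The second route needs negative cytology, with a positive cystoscopy whose biopsy shows only low-grade Ta or non-malignant tissue.

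**The planned biopsy.** Protocol 8.1.1.1 says that "biopsy for confirmation of complete response for participants with CIS should be performed at the 24 week disease assessment", or at Week 12 where that is the institution's routine. It foresees a bad result: "if the bladder biopsy collection at the Week 12 disease assessment fails to confirm CR, the biopsy collection must be repeated" at Week 24. If the biopsy cannot be done by Week 24, it moves to the next scheduled assessment.

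**Text pointing the other way.** In protocol Table 2 and SAP Table 10, the row for persistence of CIS is glossed as non-CR and marked as an EFS event. Protocol 4.1.1 describes "Participants with CIS at randomization that is not responding within 6 months of initiating study intervention, following induction or re-induction (persistence of CIS") with no cystoscopy or cytology condition. Protocol 7.1 withdraws participants with CIS from study treatment if they have no CR within 6 months.

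**The concern.** The first CR route pairs a biopsy with clear cystoscopy and cytology. The plan therefore schedules a biopsy in participants for whom both other tests may be negative, and it accepts that the biopsy may not confirm CR. If the biopsy then shows CIS, the most direct evidence of failure is in hand, but the written definitions do not make it an event, because neither of the other tests is positive.

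This bears on the primary endpoint. Read literally, a biopsy-proven failure becomes a censored observation in EFS while the same person is a non-responder in the CR analysis (SAP 6.2.2.5). Read through Tables 2 and 10, the same record is an event. Without a single rule, sites, programmers and central reviewers could classify identical records differently in an open-label trial.

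**Working it through.** **1. All test combinations at the CR biopsy**, classified by the CR and persistence rules in SAP 5.2.12:

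| Cystoscopy | Cytology | Biopsy | Result |
|---|---|---|---|
| negative | negative | non-malignant | CR |
| negative | negative | CIS | **no category** |
| negative | positive | non-malignant | no category |
| negative | positive | CIS | persistence |
| positive | negative | non-malignant | CR |
| positive | negative | CIS | persistence |
| positive | positive | non-malignant | no category |
| positive | positive | CIS | persistence |

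The second row is the subject here. The other two unclassified rows have no malignancy on biopsy and are a separate matter.

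**2. The second row followed through the plan.**
- High-grade recurrence and progression: not met, because both also need a positive cystoscopy or cytology.
- No evidence of disease: reserved for participants without CIS.
- Adequate assessment (SAP 5.2.11): the record is none of the listed outcomes.
- SAP Table 11: with no event, EFS is censored at the last adequate visit that showed no event. For a participant with CIS who never reached CR there may be no such visit, and the table does not spell out the date.
- Later follow-up: protocol 4.1.1 moves participants with persistence of CIS to telephone survival contact. If the site treats the participant that way, a later disease event may never be recorded.
- Sensitivity analyses (SAP 6.2.2.3): those on EFS events keep the Table 10 event definitions. Supportive Estimand 1 re-dates only participants already classified as persistent.

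The gap narrows in one case. The estimand (SAP 2.2.1) dates persistence at its first observation if CR is not seen after re-induction. A re-induced participant whose Week 12 record already met the definition is arguably an event by that rule. The gap is clearest when no earlier record met the definition.

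**3. Size.** The plan's own figure first. With 174 events, HR 0.69 and 1-sided 0.025 (SAP 5.1.1), power = Φ(√174/2 × |ln 0.69| − 1.960) = Φ(6.596 × 0.3711 − 1.960) = Φ(0.487) = 68.7%, as stated.

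Neither document gives a rate for CIS seen on biopsy only. An illustration:
- Participants with CIS per arm: 250/3 = 83.3 (the planned minimum).
- Assumed without CR at Week 24: 15% to 30%.
- Assumed share of those with CIS on biopsy only: 5% to 20%.
- Low: 83.3 × 0.15 × 0.05 = 0.6 per arm. High: 83.3 × 0.30 × 0.20 = 5.0 per arm.
- Expected EFS events per arm: 261/3 = 87. Shares: 0.6/87 = 0.7% and 5.0/87 = 5.7%.

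At the high end, 10 participants are affected per two-arm comparison. If they come on top of the 174 events, power at 184 is Φ(6.782 × 0.3711 − 1.960) = 71.1%. If they are already within the 174 and are lost, power at 164 is Φ(6.403 × 0.3711 − 1.960) = 66.1%.

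**The case against.** The best reply is that the plan already counts this case. The estimand refers to events as defined in Table 10, and that table and protocol Table 2 gloss persistence of CIS as non-CR. Protocol 4.1.1 uses the same label for CIS that has not responded by 6 months. This is good evidence of intent, but it does not close the gap. Persistence of CIS is a defined term with stated required evidence, and SAP 5.2.11 keeps a separate not-evaluable state, so the gloss cannot turn every non-CR into an event. What stands is that the documents conflict; they do not lay down a settled rule to discard these failures.

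Two further replies have weight. The Appendix 9 decision diagram, which protocol 8.1.1 makes the working algorithm, is not in the text available for this review and may show this branch; the written definitions would still have to match it. And the primary endpoint is investigator-assessed: an investigator holding a CIS-positive Week 24 biopsy may simply record persistence, so loss of the event is possible but not certain.

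A reader might also infer that high-grade recurrences after CR are being dropped in the same way. The wording has the same precondition, but no routine biopsy is planned after CR, and SAP 2.1 confirms that biopsy is not required at each visit. Before CR, the recurrence rule bears mainly on participants with CIS and concurrent papillary disease. The effect of that limb is small.

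**Conclusion.** The point holds as an inconsistency in the primary endpoint. Under SAP 5.2.12, SAP 5.2.11 and Appendix 9, a Week 24 record with CIS on biopsy and both other tests negative is not CR, not a defined event and not adequate, while Tables 2 and 10 and protocol 4.1.1 indicate that it was meant to count. It should be corrected.

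The number affected is unknown. The 0.6 to 5 per arm rests on the planned minimum of 250 participants with CIS and on two assumed rates that appear in neither document; the low end is less than one participant per arm.

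Two stronger conclusions are tempting and unsupported. One is that the hazard ratio is biased: nothing in the documents shows that biopsy-only CIS differs in frequency between arms. The other is that any CIS-positive biopsy after induction should be an event. Week 12 biopsy is done only where it is routine, and protocol 8.1.1.1 says that if it does not confirm CR, "the biopsy collection must be repeated at the Week 24 disease assessment". Such a rule would create Week 12 events only because a site takes biopsies early.

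**What to change.** Reconcile SAP 5.2.12, SAP 5.2.11 and protocol Appendix 9 (text and diagram) with protocol Table 2 and SAP Table 10. State, for endpoint classification only:

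- In Cohort A participants with CIS, a biopsy positive for CIS at the Week 24 CR assessment, or at the next scheduled assessment if the biopsy is delayed, is persistence of CIS whatever the cystoscopy and cytology results.
- When both are negative, the event is dated at the biopsy. The estimand's existing dating rule for persistence already documented before re-induction is unchanged.
- The visit counts as an adequate post-baseline assessment.
- A Week 12 biopsy positive for CIS with negative cystoscopy and cytology, followed by CR at Week 24, is not made an event by this change.

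The high-grade recurrence wording can be aligned for consistency. Nothing here alters treatment, re-induction, discontinuation or the biopsy schedule.

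The cost is wording in two documents and one derivation edit. Biopsy results are already on the Oncology Biopsy eCRF. Timing needs care: the SAP version is dated 10 December 2024, and the EFS cut-off was planned for about 3 years after the last randomization on 16 November 2021. SAP section 2 requires a protocol amendment for major changes to the primary endpoint definition. The clarification should be documented before anyone deciding it sees results by arm.

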### 6.1. Primary Endpoint(s)

#### 6.1.1. Event-free survival as assessed by investigator (Cohort A only)

##### 6.1.1.1. Primary analysis (for Arm A vs Arm C)

Refer to [Section 2.2.1](#) for the primary estimand.

In this study, disease may be assessed through cytology, cystoscopy, biopsy, and imaging scans conducted at screening (required), every 12 weeks for 2 years following randomization, and every 24 weeks thereafter until first occurrence of progression of disease, recurrence of high-grade disease, or persistence of CIS (for participants with CIS at baseline) regardless of initiation of subsequent anti-cancer therapy.

EFS is defined as the time from randomization until progression of disease, recurrence of high-grade disease, persistence of CIS, or death due to any cause, whichever occurs first.

An event is as defined in Table 10. The censoring and event date options to be considered for the EFS analysis ([Section 2.2.1](#)) are presented in Table 11.

$$\text{EFS (months)} = [\text{date of event or censoring} - \text{date of randomization} + 1]/30.4375$$

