**Table 10. Possible Clinical Outcomes for Participants With or Without CIS at Randomization and EFS Evaluation**

Population	Disease Assessment	EFS Event Y/N
Participants with CIS at randomization	Progressive disease [a] before achieving a CR for participants with CIS only at randomization	Y
	Progressive disease after achieving a CR	Y
	Recurrence of high-grade disease before achieving a CR for participants with CS and concurrent papillary disease at randomization	Y
	Recurrence of high-grade disease after achieving a CR	Y
	Persistence of CIS (non-CR) [b]	Y
	Recurrence of low-grade disease	N
Participants without CIS at randomization	Progressive disease	Y
	Recurrence of high-grade disease	Y
	Recurrence of low-grade disease	N

[a] Including appearance of new high-grade Ta or T1 disease for participants with CIS only at randomization.

[b] Persistence of CIS after induction, with CR after re-induction is not considered an event.

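### For participants with CIS plus papillary disease, SAP 5.2.12 calls high-grade disease before CR both recurrence and progression, and the EFS event tables have no row for progression before CR.

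*SAP*

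**What the plan says.** **Disease definitions.** The recurrence paragraph of SAP 5.2.12 lists three situations that count as recurrence of high-grade disease (high-grade Ta, T1 or CIS). The third is re-appearance "before CR for participants with CIS and concurrent papillary disease at baseline in Cohort A or B1". The paragraph then gives a tie rule, "If recurrence of high-grade disease occurs at the time of progression, progression should be the event", and closes with a sentence in two halves. The first half deals with the time after response: "For participants with CIS at randomization, appearance of high-grade disease after a CR is considered recurrence of high-grade disease". The second half deals with the time before it, for the same participants, and reads "while appearance of high-grade disease before a CR is progression".

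The progression list that follows in 5.2.12 has five bullets. Lamina propria invasion, T2 or higher, nodal disease and metastatic disease carry no limit by type of CIS. Only the last bullet, new high-grade Ta or T1 before CR, is limited to participants with CIS only. Protocol Appendix 9 (10.9) gives the same recurrence and progression definitions but does not contain the closing sentence.

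**Event table.** SAP 6.1.1.1 states "An event is as defined in Table 10", and the estimands in SAP 2.2.1 to 2.2.3 refer to the same table. Its first three rows for participants with CIS are:

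- "Progressive disease [a] before achieving a CR for participants with CIS only at randomization"
- "Progressive disease after achieving a CR"
- "Recurrence of high-grade disease before achieving a CR for participants with CS and concurrent papillary disease at randomization" (CS is evidently a typing error for CIS)

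High-grade recurrence after CR and persistence of CIS follow as events, and low-grade recurrence as a non-event. Protocol Table 2 has the same rows.

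**Outputs.** SAP 6.1.1.1 tabulates event types by arm, with progression and recurrence counted separately. After Table 12 it classifies progression events as metastatic, muscle-invasive or stage progression, the last defined as high-grade Ta or T1.

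**The concern.** There are two linked faults in the definition of the primary endpoint. First, one paragraph gives two labels to the same finding in the same participants, so the reported split between progression and recurrence depends on which sentence is applied. Second, the table named as the event definition leaves out progression before CR for one group of participants with CIS. The trial is open-label with an investigator-assessed primary endpoint, so each disease finding should have a single, stated classification before arm-level data are summarised.

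**Working it through.** No stated figure is in dispute, so the check sets the texts side by side.

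**Step 1. Coverage of Table 10 (Table 2 is the same).**

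| Baseline disease | Progression before CR | Progression after CR | High-grade recurrence before CR | High-grade recurrence after CR |
|---|---|---|---|---|
| CIS only | event | event | no row; footnote [a] makes new high-grade Ta or T1 progression | event |
| CIS plus papillary | **no row** | event | event | event |

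For CIS only, the blank is explained by the footnote. For CIS plus papillary disease, progression before CR is the one empty cell and nothing explains it.

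**Step 2. How each text classifies findings before CR in CIS plus papillary disease.**

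| Finding | Item 3 | Closing sentence | Progression list | Table 10 |
|---|---|---|---|---|
| High-grade Ta re-appears | recurrence | progression | not progression (last bullet is CIS only) | row exists only as recurrence |
| T1 where baseline papillary disease was Ta | recurrence | progression | progression (lamina propria invasion) | no row once the tie rule selects progression |
| T2 or higher, N+, M1 | not covered | not covered | progression | no row |

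The first line shows the contradiction most clearly. Item 3, the CIS-only limit on the last progression bullet, the third row of Table 10 and protocol 10.9 all point to recurrence. The closing sentence alone points to progression. The SAP version history records that version 4 narrowed the progression rule to CIS only, so the sentence may be a leftover. That is an inference, and the point does not depend on it.

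The tie rule does not resolve this. If the closing sentence holds, progression takes precedence, the recurrence row for CIS plus papillary disease would never be used, and these events would fall into the empty cell.

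The second and third lines show that the gap in the table exists even without the closing sentence.

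**Step 3. Does the primary result depend on it?** The prose in SAP 3.1 and 6.1.1.1 counts any progression and any high-grade recurrence, so either label gives an EFS event. The event date is the earliest positive biopsy, cystoscopy or cytology under both labels. Progression also admits the imaging date, so a date could differ slightly.

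**Step 4. Scale if Table 10 were programmed literally.** Under the Schoenfeld formula, power = Φ(|ln HR| × √d / 2 − z).

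- Plan (SAP 5.1.1): HR 0.69, d = 174, one-sided 0.025. 0.3711 × 13.191 / 2 − 1.960 = 0.487, giving 68.7%, as stated.
- Assumed loss of 1 event: d = 173 gives 68.5%.
- Assumed loss of 10 events: d = 164 gives 66.1%.

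The range of 1 to 10 is an assumption. The documents give no count of such events.

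**The case against.** The strongest reply is that Table 10 is not an exhaustive list. It has no row for death either, yet death is an EFS event in every definition. Its column is headed as a disease assessment, and it has to be read with the prose. The prose covers the empty cell: SAP 3.1 and 6.1.1.1 count progression without limit, 5.2.12 puts no CIS restriction on T2 or higher, N+ or M1 disease, and 5.2.11 accepts progression as an adequate assessment in all participants. On the label, investigators classify disease under protocol 10.9, which has one rule for this group.

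Most of this stands. A reader might infer from the empty cell that the primary endpoint omits the most serious early outcomes in participants with CIS plus papillary disease. The documents do not support that, for the reasons just given. A reader might also try to size the problem by applying a guessed share with papillary disease to the minimum of 250 participants with CIS. No share is given, and the product would count everyone in the subgroup rather than the events whose label or inclusion is in doubt.

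Two things remain. Death is not a disease assessment, so its absence does not explain a row that expressly restricts progression to CIS only. And the closing sentence of 5.2.12 is a stated rule in the SAP, broader than and contrary to item 3 of its own paragraph.

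**Conclusion.** The SAP is wrong as written on a point of classification. It gives two labels to high-grade disease before CR in participants with CIS plus papillary disease, and both event tables lack a row for progression before CR in that group.

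If the prose definition is followed, the number of EFS events should not change, and neither should the log-rank test or hazard ratio, apart from possible small date differences through imaging. The direct effect is on the by-arm counts of progression against recurrence and on the stage-progression line of the progression-type table.

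Loss of events is a risk only under literal programming of Table 10. Most of the EFS sensitivity analyses in SAP 6.2.2.3, including the one based on BICR, use the same table and would not expose such an error. The number of participants affected cannot be derived from the documents.

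**What to change.** 1. In SAP Table 10 and protocol Table 2, remove the restriction to CIS only from the first row, so that it covers progression before CR in all participants with CIS. Footnote [a] already carries the CIS-only rule for new high-grade Ta or T1. Correct CS to CIS in the third row of Table 10.
2. In the last sentence of the SAP 5.2.12 recurrence paragraph, limit the second clause to new high-grade Ta or T1 in participants with CIS only. This matches the last progression bullet, item 3 and protocol 10.9. It also avoids labelling CIS found before CR as progression, since the paragraph counts CIS as high-grade disease.
3. Confirm that the EFS derivation program and the event-type and progression-type tables follow the reconciled text.

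The cost is two substantive wording edits, one typing correction and a program check. No new data are needed.
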